### Benefits

We anticipate that subjects on active treatment will have improved quality of life due to lessening ataxia given the preliminary findings in previous studies. From a scientific standpoint, we anticipate that this study will evaluate the efficacy of acetazolamide as a therapeutic agent for ataxia in PMM2-CDG.

## Risk/Benefit Assessment

The risks to subjects are reasonable in relation to the anticipated benefits because the major risks are not universal, closely monitored for, and would lead to study withdrawal. The majority of the risks can be treated medically and are likely to resolve after discontinuing therapy. The potential benefits for participating subjects and medical knowledge are clinically significant. Amelioration in ataxia will significantly improve the subject's quality of life, and possibly allow for downstream gains in learning and development. The gain in knowledge will allow for healthcare providers to make informed decisions about utilizing this therapeutic in this population. It may also be the groundwork needed to add an FDA-approved indication for the use of acetazolamide in PMM2-CDG. This would be the first FDA-approved therapeutic agent for PMM2-CDG, which would be a major breakthrough for this disease and other closely related ultra-rare genetic disorders.

## 2 Study Objectives

### **Objective 1 (Primary):**

**To evaluate the efficacy of acetazolamide in improving ataxia in patients with PMM2-CDG.**

To achieve this goal, we will compare the change of Mini-ICARS score from baseline to after six months post-randomization of treatment between the placebo and active treatment groups.

### **Objective 2 (Secondary):**

**To evaluate for any adverse events related to longer term acetazolamide administration.**

To achieve this goal, we will monitor changes on physical exam, laboratory studies that are likely to be affected by acetazolamide therapy including blood pH and electrolyte balance, and urine calcium excretion regularly through the duration of the trial. We will determine the percentage of patients treated with acetazolamide who experience (a) drug related adverse event(s) and (b) drug related serious adverse event(s) while they are on blinded therapy as well as for the duration they remain in the open label extension.

### **Objective 3 (Secondary):**

**To examine the effect of acetazolamide on PMM2 biomarkers including carbohydrate deficient transferrin, electrolytes (Na, K, Cl, CO2), VBG (pH, pCO2, PO2, CO2, Base excess) or bicarbonate/CO2, liver function tests (AST, ALT, GGT, indirect and direct bilirubin, total protein, albumin, alkaline phosphatase), kidney function tests (BUN, Creatinine, Urinalysis, urine calcium/creatinine ratio, urine protein/creatinine ratio), growth (height, weight, head circumference), vital signs (blood pressure, respiratory rate, heart rate), PROMIS scores, dysarthria using the PATA score, and NPCRS score.**

We will collect these data at baseline and after 6 months of placebo or treatment and identify changes from baseline. We will analyze if there is a difference of changes between the treatment and placebo group. We will also compare baseline measurements to the last measurement obtained as part of the open label extension and determine if there are changes to these measurements.

### **Objective 4 (Secondary):**

**To explore characteristics of individuals with PMM2-CDG who do not respond to acetazolamide.**

In addition to analyzing our data for effect, we will perform subgroup analysis based on genotype, ataxia severity, baseline NPCRS score, sex, concomitant therapies, results of transferrin isoform analysis, concomitant medical problems/diagnoses, number of previous hospitalizations, ages at diagnosis, baseline laboratory test results, age at developmental milestones achievement, baseline developmental/educational achievement, baseline frequency and type of therapies, and baseline support needed for activities of daily living to determine if there are particular subgroups that are less responsive to therapy.

### **3 Study Design**

#### **3.1 General Description**

This study is a double-blind, placebo-controlled, 1:1 randomized clinical therapeutic trial of acetazolamide for the treatment of ataxia in patients with PMM2-CDG. Clinical history and screening data will be reviewed to determine subject eligibility. Potential subjects who have biallelic pathogenic or likely pathogenic variants in PMM2 OR biallelic variants of uncertain significance, pathogenic, or likely pathogenic variants in PMM2 AND Enzymatic confirmation of PMM2 enzyme deficiency will be consented. Baseline data will be collected prior to randomization and at treatment initiation. Subjects who meet all inclusion criteria and none of the exclusion criteria will be enrolled into the study. Each subject who meets all the inclusion and none of the exclusion criteria will then be randomized to placebo or acetazolamide. They will be administered weight-dependent doses of acetazolamide or an equivalent dose of placebo twice daily by mouth. Initial dose of acetazolamide is at least 7.58 mg/kg/day per Table 1 . If the pH is <7.3 and/or bicarbonate <21, a value associated with mild metabolic acidosis, the dose will be reduced per table 1. Subjects will be randomized after Visit 1, will initiate blinded therapy within the first week, and will continue on prescribed/adjusted blinded treatment until Visit 4. Of note, the volume or number of capsules will be adjusted based on tolerance as assessed by symptoms and laboratories. If an individual is randomized to the placebo arm, the initial number of capsules will be as per Table 1, and number of capsules will also be adjusted based on symptoms and laboratory values each time dose adjustment is planned. Open label period will then begin after Visit 5 up to Visit 9 (see Figure 1 and Table 3). As both the subject and investigator do not know if the subject received placebo or acetazolamide, the dose of acetazolamide will be started at Visit 5 per table 1 and titrated upwards in the same manner in Visits 6, 7 and 8 (remote) as in Visits 2, 3 and 4 (remote). Subjects will have the option to withdraw from the study any time after Visit 5 if they do not wish to proceed onto or continue with the open label phase.

#### **3.2 Number of Subjects**

We aim to enroll 26 evaluable patients. Up to 7 additional patients will be enrolled to account for a 20% loss in sample size due to ineligibility, major treatment violation, cancellation, or withdrawal prior to completion of the 6-month blinded phase of the study. Maximum projected accrual is, therefore, 33 patients. Enrollment will continue until the 26th evaluable patient completes the blinded phase. Enroll will pause when 26 patients have either completed or are

actively completing the blinded phase; enrollment will reopen if any of these patients withdraw before completing the blinded phase.

### 3.3 Duration of Participation

The duration of participation is a maximum of approximately 1.75 years as outlined in Figure 1 below.

[figure not shown]

Figure 1. Study Timeline for visits 1 through 9

### 3.4 Primary Study Endpoints

Primary Endpoint: Change in Mini-ICARS score from baseline to 6 months.

### 3.5 Secondary Study Endpoints

Secondary Endpoints: Biomarkers, testing scores, and rating scales at 6 months. These biomarkers and scores include carbohydrate deficient transferrin results (Mono/Di, A/Di, Apo CIII1/Apo C III2, Apo CIII0/Apo CIII2), electrolytes (Na, K, Cl, CO2), VBG (pH, pCO2, PO2, CO2, Base excess) or bicarbonate/CO2, liver function tests (AST, ALT, GGT, indirect and direct bilirubin, total protein, albumin, alkaline phosphatase), coagulation factors (prothrombin time, coagulation factor XI, and antithrombin), kidney function tests (BUN, Creatinine, Urinalysis, urine calcium/creatinine ratio, urine protein/creatinine ratio), bone mineral metabolism markers (serum bone-specific alkaline phosphatase (BSAP) and carboxy-terminal collagen crosslinks (CTX), Calcium, Phosphorus, Vitamin D, and parathyroid hormone (PTH)), growth (height, weight, head circumference), vital signs (blood pressure, respiratory rate, heart rate), PROMIS scores, the PATA score, and NPCRS score.

### 3.6 Primary Safety Endpoints

The primary safety endpoint is incidence of (a) drug related adverse event(s) and (b) drug related serious adverse event(s) while patients are on blinded therapy as well as for the duration they remain in the open label extension.

### 3.7 Identification of Source Data

The following data will be collected:

- Date of visit
- Age at visit (Years, Months, Days)
- Vital signs: systolic and diastolic blood pressures (mmHg), heart rate (beats/minute), respiratory rate (breaths/minute), temperature (degrees C)
- Growth Data: length/height (cm), weight (kg), head circumference (cm)
- Physical Exam: brief neurologic exam, cardiovascular exam, abdominal exam, (HEENT) head ears eyes nose throat exam, dermatologic exam, pulmonary exam, musculoskeletal exam (Normal/Abnormal with text field to explain abnormality)
- PATA score
- AE and SAEs defined by the CTCAE version 5 (specific AE/SAE and date; see Appendix D)
- PROMIS Questionnaires (Appendix C)
- Mini-ICARS (Appendix B)
- NPCRS (Appendix A)
- Drug volume prescribed (ml/day or number of capsules/day)
- Laboratory values, normal ranges, and units: CBC (WBC, Hgb, Hct, Plt, % Neutrophils, % Lymphocytes, % Eosinophils, % Basophils, % Monocytes, % Bands, MCV, MCHC, MCH), electrolytes (Na, K, Cl, CO2), VBG (pH, pCO2, PO2, CO2, Base excess) or bicarbonate/CO2, liver function tests (AST, ALT, GGT, indirect and direct bilirubin, total protein, albumin, alkaline phosphatase), coagulation factors (prothrombin time, coagulation factor XI, and antithrombin), kidney function tests (BUN, Creatinine, Urinalysis, urine calcium/creatinine ratio, urine protein/creatinine ratio)
- BSAP, CTX, calcium, phosphorus, vitamin D, and PTH at baseline and visit 5.
- Plasma/Serum Acetazolamide level at visit 5.
- Physical therapy, Occupational therapy, Speech therapy, Feeding therapy – (yes/no if ongoing, number of sessions per month)
- Annual screening ophthalmological exam including intraocular pressure testing.

The following source data will be captured in supportive documentation (e.g. study source documents, EMR):

- Clinical interpretation of laboratory values
- Medication review and adherence
- Video of the Mini-ICARS assessment

## 4 Subject Selection Enrollment and Withdrawal

### 4.1 Inclusion Criteria

- At minimum, 4 years of age at Visit 1
- Biallelic pathogenic or likely pathogenic variants in PMM2  
OR  
Biallelic variants of uncertain significance, pathogenic, or likely pathogenic variants in PMM2 AND Enzymatic confirmation of PMM2 enzyme deficiency
- Affected with ataxia evidenced by Mini International Cooperative Ataxia Rating Scale (Mini-ICARS) score >0 at baseline
- Parent or legal guardian available to provide consent on behalf of minor subjects or adult subjects who are unable to give informed consent due to developmental disabilities. Willingness of subject or legal guardian to provide consent.
- If female and >10 years old, willing to practice abstinence or using an effective contraceptive regimen that is constituted by two acceptable effective methods of contraception, including a barrier method such as a condom or occlusive cap (diaphragm or cervical/vault cap) with spermicidal foam/gel/film/cream/suppository and an established non-barrier method such as oral, injected, or implanted hormonal methods, an intrauterine device (IUD), or intrauterine system for the entire duration of the treatment period and for at least 28 days after receiving the last study drug dose. Sterilized or infertile subjects (defined as having undergone surgical sterilization, ie, bilateral tubectomy, hysterectomy and bilateral ovariectomy or as being postmenopausal, defined as at least 12 months of amenorrhea prior to enrollment) will be exempted from the requirements to use contraception in this study.

### 4.2 Exclusion Criteria

- Hepatic impairment defined as AST/ALT >3.0 - 5.0 x ULN if baseline was normal; >3.0 - 5.0 x baseline if baseline was abnormal in the last 12 months
- Renal impairment defined as serum creatinine 1.5-1.9 times ULN for age OR  $\geq 26.5$  umol/l increase from ULN for age
- Hypokalemia
- Hyponatremia
- Hyperchloremic acidosis
- Adrenal insufficiency
- Hypersensitivity to acetazolamide
- Hypersensitivity to any of the components of the placebo
- History of treatment with experimental drug within 28 days of Visit 1
- Currently taking Mecamylamine, Sodium Phosphates, Salicylates, Mefloquine, Methenamine, other Carbonic Anhydrase Inhibitors, Phenytoin, Primidone, folic acid antagonists, antidiabetic agents, quinidine, lithium, cyclosporine, sodium bicarbonate.

- Participation in another therapeutic trial - the subject will not be permitted to participate in any other drug trial during the blinded phase and during the 28 days prior to Visit 1
- Pregnant (positive urine beta-HCG test) or nursing (by history) women
- Weight <10 kg

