Diagnosis and Main Inclusion/Exclusion Criteria	
Inclusion criteria:
 
 
1. Biallelic pathogenic or likely pathogenic variants in PMM2 OR Biallelic variants of uncertain significance, pathogenic, or likely pathogenic variants in PMM2 AND Enzymatic confirmation of PMM2 enzyme deficiency
 
2. Age <math>\geq 4</math> years old, and
 
3. Affected with ataxia evidenced by mini International Cooperative Ataxia Rating Scale (Mini-ICARS) score <math>>0</math> at baseline.
 
 
Exclusion criteria:
 
 
1. Hepatic impairment defined as AST/ALT <math>>3.0 - 5.0 \times</math> ULN if baseline was normal; <math>>3.0 - 5.0 \times</math> baseline if baseline was abnormal
 
2. Renal impairment defined as serum creatinine 1.5-1.9 times ULN for age OR <math>\geq 26.5 \text{ umol/l}</math> increase from ULN for age
 
3. Hypokalemia
 
4. Hyponatremia
 
5. Hyperchloremic acidosis
 
6. Adrenal insufficiency
 
7. Hypersensitivity to acetazolamide
 
8. Hypersensitivity to any of the components of the placebo
 
9. History of treatment with experimental drug within 28 days of Visit 1
 
10. Currently taking Mecamylamine, Sodium Phosphates, Salicylates, Mefloquine, Methenamine and other Carbonic Anhydrase Inhibitors
 
11. Weight <math><10 \text{ kg}</math>
 

Study Product, Dose, Route, Regimen	
Acetazolamide or Placebo
 
Acetazolamide capsules <math>\leq 30 \text{ mg/kg/day}</math> divided BID or matching placebo, divided BID daily, by mouth.
 
Due to the potential of subject intolerance, we will start patients on a lower dose divided BID and titrate up in a stepwise manner per table 1 if well tolerated with no AEs or abnormal pH. If the pH is <math><7.3</math> and/or bicarbonate <math><21</math>, the dose will be reduced by <math>7\text{mg/kg/day}</math>.

Duration of Administration	12 months (52 weeks) total, 6 months (26 weeks) blinded, 6 months (26 weeks) open label extension
Reference therapy	Placebo

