### 1.2 Investigational Agent

## Acetazolamide

Acetazolamide is a potent carbonic anhydrase inhibitor, effective in the control of fluid secretion, in the treatment of certain convulsive disorders, and in the promotion of diuresis in instances of abnormal fluid retention. Acetazolamide is not a mercurial diuretic. Rather, it is a nonbacteriostatic sulfonamide possessing a chemical structure and pharmacological activity distinctly different from the bacteriostatic sulfonamides. Acetazolamide is an enzyme inhibitor that acts specifically on carbonic anhydrase, the enzyme that catalyzes the reversible reaction involving the hydration of carbon dioxide and the dehydration of carbonic acid. Evidence seems to indicate that Acetazolamide has utility as an adjuvant in the treatment of certain dysfunctions of the central nervous system (CNS). Inhibition of carbonic anhydrase in this area appears to retard abnormal, paroxysmal, excessive discharge from CNS neurons. The diuretic effect of acetazolamide is due to its action in the kidney through the reversible reaction involving hydration of carbon dioxide and dehydration of carbonic acid. This reaction results in renal loss of HCO3 ions, which also carries out sodium, water, and potassium, leading to alkalinization of the urine and promotion of diuresis. Alteration in ammonia metabolism occurs due to increased reabsorption of ammonia by the renal tubules as a result of urinary alkalinization.

It is a white to faintly yellowish white crystalline, odorless powder, weakly acidic, very slightly soluble in water and slightly soluble in alcohol. The chemical name for acetazolamide is N-(5-Sulfamoyl-1,3,4-thiadiazol-2yl)-acetamide. As a carbonic anhydrase inhibitor that changes the intracellular pH, acetazolamide affects the transmembrane potential and conductance of potassium and calcium channels (Bain et al. 1992, Sappey-Marinier et al. 1999). While it has been studied more extensively in adults, it has been safely administered to children for a variety of indications at doses that range from 4 mg/kg/day to the lower of 100 mg/kg/day or 4000 mg/day (Moffett et al. 2007, Distelmaier et al. 2006, Hacifazlioglu et al. 2012, Ko et al. 2010, Park et al. 2014, Per et al. 2013, Rangwala et al. 2007, Reiss et al. 1996, Soler et al. 1998, Spennato et al. 2011, Standridge et al. 2010).

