Acetazolamide is an FDA-approved drug for adults for treatment of glaucoma, epilepsy, altitude sickness, and edema. FDA approved doses are in adults 250 to 1000 mg/day divided once to four times daily. A documented off-label use is for treatment of familial periodic paralysis. While the regular-release capsule is not FDA approved in children, it is used commonly in clinical practice and recommended doses have been established in children for management of glaucoma and seizures, reversal of metabolic alkalosis, and prevention and treatment of altitude sickness at 10-30 mg/kg/day given in one to four divided doses. The extended released capsule is FDA-approved in children with a max dose of 30 mg/kg/day or 1000 mg/day (Acetazolamide, 2020).

Acetazolamide is contraindicated in cases of marked liver disease or dysfunction and in patients with cirrhosis because of the risk of development of hepatic encephalopathy and electrolyte imbalance. It is also contraindicated in patients with severe renal disease as it may potentiate acidosis and may cause CNS adverse effects in dialysis patients. It is contraindicated for individuals with carbonic anhydrase inhibitor hypersensitivity, sulfonamide hypersensitivity, electrolyte disturbances, and adrenal insufficiency. It has been reported to occasionally induce

bone marrow suppression and blood dyscrasias. It is an FDA pregnancy risk category C. These contraindications are reflected in our study exclusion criteria.

In this study, regular-release acetazolamide will be dispensed in compounded capsule and compounded liquid formulations.

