## 1.5 Risks and Benefits

### Risks

In general, acetazolamide is considered a safe drug. Per the package insert, severe adverse reactions that have been reported with administration of acetazolamide include seizures, muscle paralysis, hepatic necrosis, hepatic failure, hepatic encephalopathy, toxic epidermal necrosis, agranulocytosis, anaphylaxis, aplastic anemia, hemolytic anemia, Stevens-Johnson syndrome, pancytopenia, acute generalized exanthematous pustulosis, renal failure, and renal tubular obstruction. The incidence of each reaction is unknown. It is likely that individuals who have significant baseline allergy to acetazolamide and other components, hepatic dysfunction, blood dyscrasias, and/or renal dysfunction would be at higher risk for these severe reactions. Thus we are assessing for hepatic dysfunction, renal dysfunction, allergy, and blood dyscrasias at baseline and excluding individuals with significant disturbances in their laboratory assessments or have a history of allergy to the components of the therapeutic agent or placebo (as defined by the exclusion criteria below). We will monitor complete blood count (CBC), liver function tests (LFT), venous blood gas (VBG or bicarbonate/CO2), electrolytes, and creatinine, and urinalysis with urine creatinine, calcium, and protein at baseline and regularly throughout the study, and if any individual meets exclusion criteria at any point during the study, we will terminate their treatment. Patients may develop acidosis on acetazolamide therapy, which may lead to inability to continue the therapy longer or a decrease in dosage. Acetazolamide has been associated with growth suppression in pediatric patients, although not all individuals have been reported to have poor growth and the dosages associated with growth suppression have not been consistent. Growth has been reported to resume and improve after discontinuation of acetazolamide. We will monitor growth parameters (height, weight, head circumference) regularly throughout the study and tailor their management and continuation in the study on a case by case basis. We will monitor patients' acid/base status and titrate acetazolamide accordingly. We will also obtain a one-time measurement of acetazolamide serum concentration at steady state at the six-month visit.

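### Section 4.2 omits the sulfonamide and carbonic anhydrase inhibitor hypersensitivity exclusions that Section 1.2 says it contains, and the hepatic exclusion and stop criterion, read literally, ends at 5 x

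*Combined protocol and SAP*

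**What the plan says.** **Hypersensitivity.** Section 1.2 names marked liver disease and severe renal disease as contraindications, then adds "carbonic anhydrase inhibitor hypersensitivity, sulfonamide hypersensitivity, electrolyte disturbances, and adrenal insufficiency". After noting reported blood dyscrasias and the pregnancy category, it concludes: "These contraindications are reflected in our study exclusion criteria".

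The Study Summary has item "7. Hypersensitivity to acetazolamide", followed by an item on placebo components. Section 4.2 has the same two entries, the second being "Hypersensitivity to any of the components of the placebo". Section 1.5 describes the allergy exclusion as covering the components of the drug or placebo and refers to the same criteria for its definition. Other carbonic anhydrase inhibitors do appear in 4.2, but only among medicines a patient may not be taking at entry.

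**Liver.** Section 4.2 has "Hepatic impairment defined as AST/ALT >3.0 - 5.0 x ULN if baseline was normal", and the same 3.0 to 5.0 range as a multiple of baseline where baseline was abnormal. The Study Summary, Section 8.1 (Abnormal Laboratory Values) and Section 8.5 use the same band. Sections 8.1 and 8.5 stop the drug when these values occur and no other cause is likely. Section 4.3 points to 8.1 for its stop rule. Section 1.5 ends treatment for anyone who meets an exclusion criterion during the study, so the entry band also operates on study.

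**The concern.** These criteria decide who may start the drug and who must stop it.

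On the first point, a patient with a known sulfonamide allergy who has never taken acetazolamide meets no listed exclusion, although the protocol calls the drug contraindicated for that patient. Section 1.5 lists anaphylaxis, Stevens-Johnson syndrome and toxic epidermal necrosis among the severe reactions reported.

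On the second, the literal text requires a stop at the milder liver value and only a judgement at the worse one. Section 1.2 says "Acetazolamide is contraindicated in cases of marked liver disease or dysfunction and in patients with cirrhosis", so the range left out is the one the contraindication is chiefly about.

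**Working it through.** No figure in the plan needs reproducing. The check is a comparison of texts plus an interval check.

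**Step 1. Contraindications against the exclusion list.** Section 1.2 gives six groups; Section 4.2 has 13 bullets.

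| Group in Section 1.2 | Own entry in 4.2? |
|---|---|
| Liver | Yes, AST/ALT band |
| Kidney | Yes, creatinine |
| Electrolytes | Yes, low potassium, low sodium, hyperchloremic acidosis |
| Adrenal insufficiency | Yes |
| Carbonic anhydrase inhibitor hypersensitivity | No, acetazolamide only |
| Sulfonamide hypersensitivity | No, acetazolamide only |

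Four of six are present. Two of the 13 bullets concern hypersensitivity and none names sulfonamides. In the Study Summary it is two of 11 items, and again none names sulfonamides.

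**Step 2. Could the acetazolamide entry cover the other two groups?** Section 1.2 says of acetazolamide that "it is a nonbacteriostatic sulfonamide possessing a chemical structure and pharmacological activity distinctly different from the bacteriostatic sulfonamides". An investigator reading this has no clear basis for treating an allergy to another sulfonamide as an allergy to acetazolamide. Section 3.1 randomizes everyone who meets all inclusion and no exclusion criteria, and 4.2 has no investigator-discretion entry to catch such a patient.

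**Step 3. The hepatic band.** Let x be AST/ALT divided by the applicable reference (ULN if baseline was normal, baseline if abnormal). As written, the criterion is 3.0 < x ≤ 5.0. Without the ceiling it is x > 3.0.

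| x | As written | Without ceiling |
|---|---|---|
| 2 | not excluded, no stop | not excluded, no stop |
| 4 | excluded, stop | excluded, stop |
| 8 | not excluded, no stop | excluded, stop |

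The stop under 8.1 and 8.5 also requires that no other cause is likely.

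**Step 4. What else applies above 5 x.**
- Section 8 (opening text) requires the principal investigator to re-evaluate risk after significant laboratory changes, but sets no threshold and leaves the outcome open.
- Section 4.3 allows a pause or discontinuation for hepatic failure or insufficiency; it is permissive.
- Section 8.5 has a DSMB route for an SAE above grade 3. A symptom-free AST/ALT of 8 x does not in itself meet any SAE criterion in 8.1. The laboratory-based DSMB notice in 8.5 uses the same band.
- Section 8.1 uses the band as its trigger for recording an AE. Under 8.2 a higher value would still be graded if judged clinically significant, but grading does not stop the drug.

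None of these is a mandatory stop.

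**Step 5. Creatinine, for contrast.** The renal band also has a ceiling (1.5 to 1.9 x ULN), but a second limb takes any rise of at least 26.5 umol/l over ULN. Just above 1.9 x ULN the rise is 0.9 x ULN. That reaches 26.5 when ULN ≥ 26.5/0.9 = 29.4 umol/l, and the gap is then closed. For a lower ULN a gap would remain just above 1.9 x. The documents give no ULN, so this is a consistency point only. The hepatic criterion has no second limb.

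**The case against.** The case on the other side is reasonable in several respects.

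*Clinicians will not read the band literally.* The entry is labelled hepatic impairment, and few investigators would regard 8 x as unimpaired. The provisions in Sections 4, 8, 8.2 and 8.5 give them room to act. This stands as a statement of likely behaviour. It does not make the written rule correct: three sites should not have to infer the intent of a mandatory stop.

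*Acetazolamide is itself a sulfonamide and a carbonic anhydrase inhibitor, so excluding allergy to it reflects the class.* That covers patients with a known acetazolamide reaction. It does not cover a patient who reacted to a related drug and never took this one, and Section 1.2 lists the class allergies as contraindications in their own right.

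*Adding sulfonamides would bar patients allergic only to sulfonamide antibiotics.* True, and it is a real cost in a rare disease. The breadth comes from the protocol's own contraindication. If the sponsor wants a narrower exclusion, the statement in Section 1.2 has to change.

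*Removing the ceiling does not deal with a chronically abnormal baseline.* Also true. A patient stable at 8 x ULN is at 1 x baseline and is not excluded under either wording. That is a separate question, which the change proposed here does not settle.

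*The Visit 1 interview in Section 6.1 does not list allergies by name.* Correct, but medical history is taken there and Section 7.2 already counts allergies among the baseline characteristics.

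**Conclusion.** Both parts hold. Section 1.2's statement about the exclusion criteria is wrong for two of its six contraindication groups. The hepatic criterion, written in four places with two rules resting on it (the entry exclusion, which also serves as the on-study termination rule, and the drug stop), has no limb above 5 x the applicable reference.

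The first part needs no assumption beyond the text. The second rests on a literal reading that very probably departs from what the authors intended, which makes it a drafting error in a safety rule. The documents do not say how many patients have a sulfonamide allergy or AST/ALT above 5 x, so no number affected can be given. Sample size and the primary analysis are not in question. The point should be fixed because the rule as written gives the less safe result when followed exactly, and the correction is a few words.

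**What to change.** 1. In Section 4.2 and the Study Summary, widen the acetazolamide allergy entry to *hypersensitivity to acetazolamide, other carbonic anhydrase inhibitors, or sulfonamides*. If a narrower exclusion is intended, correct the sentence in Section 1.2 and give the reason.
2. In the Study Summary and Sections 4.2, 8.1 and 8.5, write the hepatic criterion as *>3.0 x ULN if baseline was normal; >3.0 x baseline if baseline was abnormal*, with no upper limit. Keep the 12-month qualifier in 4.2. Sections 1.5 and 4.3 then follow by reference.
3. For consistency, write creatinine in the same four places as *≥1.5 times ULN for age*, keeping the 26.5 umol/l limb.

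The cost is a protocol amendment with IRB submission (Section 11) and possibly a few more exclusions. With 26 evaluable patients needed and at most 33 enrolled, each patient kept out is one more to find: 1/26 = 3.8% of the target. No new test is needed, since AST and ALT are already drawn at Visit 1. The allergy question fits within the Visit 1 medical history, and naming it there would help.
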